### ***End points***

The primary end point is the occurrence of gastric and/or duodenal ulcers, as determined by endoscopy, during the 6-month study period. An ulcer is defined as a circumscribed mucosal break at least 0.5 cm in diameter (measured using endoscopy forceps) and with a perceptible depth. Only events that are confirmed by the adjudication committee and that occurred during treatment are included in the analysis. Patients who do not have follow-up endoscopic examination are assumed to have had normal findings.

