## PATIENTS AND METHODS

### Study population

We will screen for eligible patients who have a past history of gastroduodenal ulcer and underwent endoscopy for dyspeptic symptoms or routine screening, while receiving thienopyridine(either clopidogrel or ticlopidine) therapy to prevent ischemic events. We enroll 334

patients in the study if they meet the following criteria: endoscopic examination reveals normal appearance or pictures of gastritis only; they have received thienopyridine for at least two weeks; they have an atherosclerotic disease such as ischemic heart disease or stroke; they require long-term anti-platelet therapy; and they are adult patients aged  $\geq 20$  years. Patients are excluded if they have a history of gastric or duodenal surgery other than oversewing of a perforation; if they are allergic to the study drugs; if they require long-term treatment with non-steroidal anti- inflammatory drugs (NSAIDs), corticosteroids, aspirin, or anticoagulant agents; if they are pregnant; if they have active cancer, acute serious medical illness or terminal illness; and if they have gastroesophageal reflux disease.

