### ***Follow-up***

Patients are followed up as outpatients with visits every month. Upper gastrointestinal and cardiovascular symptoms are assessed at each visit. They are asked to return to the outpatient clinic if they have persistent dyspeptic symptoms (epigastric pain, fullness, nausea or vomiting) and to report to the emergency room if they have evidences of gastrointestinal bleeding (hematemesis, melena, or sudden onset of severe epigastric pain), cardiovascular events (chest pain, syncope, or sudden onset of severe palpitation) or cerebrovascular accidents (conscious disturbance, hemiparesis, or dysphagia). Follow-up endoscopy with biopsy for urease test is performed whenever persistent dyspepsia, severe epigastric pain, hematemesis or melena occurred and at the end of the 6th month. The endoscopists who performed follow-up endoscopy are unaware of the treatment group assignments. The events of acute coronary syndrome and cerebral vascular accidents during the study period are carefully monitored and assessed.

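### An ulcer proven only at surgery, on imaging or at autopsy, in a patient with no follow-up endoscopy, is scored as no ulcer

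*Protocol*

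**What the plan says.** Four statements in the Protocol, End points, decide what counts as an event.

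- Method: "The primary end point is the occurrence of gastric and/or duodenal ulcers, as determined by endoscopy, during the 6-month study period".
- Case definition: "An ulcer is defined as a circumscribed mucosal break at least 0.5 cm in diameter (measured using endoscopy forceps) and with a perceptible depth".
- Filter: "Only events that are confirmed by the adjudication committee and that occurred during treatment are included in the analysis".
- Patients without endoscopy: "Patients who do not have follow-up endoscopic examination are assumed to have had normal findings".

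The Follow-up section says when endoscopy takes place. It is "performed whenever persistent dyspepsia, severe epigastric pain, hematemesis or melena occurred and at the end of the 6th month". Patients are also told to "report to the emergency room if they have evidences of gastrointestinal bleeding (hematemesis, melena, or sudden onset of severe epigastric pain") or for cardiovascular or cerebrovascular symptoms. The endoscopists who perform follow-up are blinded to treatment. Neither section mentions surgery, imaging or autopsy as a source of outcome information.

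**The concern.** An ulcer can be established without an endoscope. A patient with a perforation may go from the emergency room to imaging and then to theatre. A patient may die of bleeding before anyone can perform an endoscopy, and the ulcer is then seen at autopsy. If no follow-up endoscopy was done, the last sentence of the End points paragraph applies, and the patient is recorded as having normal findings.

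This differs from the usual problem of patients whose ulcer status is unknown. For them, assuming no ulcer is an imputation, and it can be examined by a different imputation or by exclusion. Here the status is known and the ulcer is documented. Neither exclusion nor imputation would count it; only a change to the case definition would. An analysis plan normally implements the protocol's case definition, so it would inherit this one.

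At stake is the accuracy of the primary outcome in a small number of clinically severe cases, and whether the result can be defended if a proven perforation or fatal bleed appears in the data as a normal finding.

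**Working it through.** **Step 1. Trace one patient through the text.** Suppose an ulcer is shown only at operation, on imaging or at autopsy, during treatment, and no follow-up endoscopy was done.

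1. Method: endoscopy is the only method named, so the ulcer does not meet the end point.
2. Case definition: the size is measured with endoscopy forceps, and no such measurement exists. The criterion cannot be met as written.
3. Filter: the adjudication committee decides which events are kept. The wording restricts the set of events and gives the committee no authority to add one established another way.
4. Patients without endoscopy: the patient is assumed normal, and no exception is stated.

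All four sentences lead to the same result: the patient is scored as ulcer-free. The first sentence alone would leave the score unstated. The last one turns it into a negative.

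**Step 2. Find who is affected.** Set End points beside Follow-up.

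| Presentation | Endoscopy required by Follow-up? | Result under End points |
|---|---|---|
| Hematemesis or melena, endoscopy done | Yes | Counts if the definition is met and adjudicated |
| Severe epigastric pain or persistent dyspepsia, endoscopy done | Yes | Counts if the definition is met and adjudicated |
| Silent ulcer present at month 6, endoscopy done | Yes | Counts if the definition is met and adjudicated |
| Ulcer seen at surgery, on imaging or at autopsy, no follow-up endoscopy ever done | Required if a trigger symptom occurred, but not done | Scored normal |

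Only the last row is misclassified.

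**Step 3. Size per case.** Inputs: 334 patients planned (Abstract; Study population) and two arms (Randomization and treatment). The allocation ratio is not stated. Assuming 1:1, n = 334/2 = 167 per arm.

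Let k be the number of such cases in an arm. The observed ulcer rate in that arm is too low by k/167:

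- k = 0: 0
- k = 1: 1/167 = 0.6 percentage points
- k = 2: 2/167 = 1.2 percentage points

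The documents do not give k. The range 0 to 2 is an assumption, chosen because such cases should be rare.

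**Step 4. Direction.** Write the risk difference as famotidine minus pantoprazole, with k_F and k_P cases lost in each arm. Then

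observed difference = true difference − (k_F − k_P)/167.

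If k_F = k_P, the difference is unchanged. If k_F > k_P, it moves against pantoprazole; if k_F < k_P, it moves in favour of pantoprazole. The documents give neither number, so the sign cannot be stated.

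**Step 5. Sample size.** The Protocol gives 334 without alpha, power, design rates or dropout. There is no stated calculation to reproduce, and the point does not depend on one.

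**The case against.** The strongest reply is that the trial already sends serious ulcers to endoscopy. Bleeding and severe epigastric pain are listed triggers, and everyone is due an endoscopy at month 6. This stands, and it limits the point to ulcers that never reach endoscopy. A reader might infer that the most serious ulcers in general become non-events. The Follow-up section rules that out.

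A second reply is that the assumed-normal sentence refers only to follow-up endoscopic examination, so an emergency endoscopy may well qualify. A patient who survives an operation is also still due the month-6 examination. Both stand. A later endoscopy removes the patient from the assumed-normal rule, although a healed ulcer might not then be visible.

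Third, a single forceps-measured definition read by blinded endoscopists is a coherent choice, and adding events without a size measurement mixes methods of ascertainment. This is a real cost, but it applies to very few events. An adjudication charter or analysis plan that is not at hand might deal with unusual evidence. The Protocol, however, does not leave the matter open: it states a rule without exception.

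Three further inferences are tempting and not supported.

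- That the Protocol expects perforations during the trial. The Study population section excludes a "history of gastric or duodenal surgery other than oversewing of a perforation". This concerns past history at entry and says nothing about expected outcomes.
- That one or two lost events would change the significance of the result. That depends entirely on the event counts assumed in each arm. The 11% six-month recurrence in the Introduction is a background figure in clopidogrel users with ulcer history, not a stated design rate; both arms here receive acid suppression, and no rate is given for either.
- That the rule hides a safety signal. An efficacy definition does not prevent serious ulcer events from being recorded, and upper gastrointestinal symptoms are assessed at every monthly visit.

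**Conclusion.** The point holds in a narrow form. As written, an ulcer documented only at surgery, on imaging of a perforation or at autopsy, in a patient with no follow-up endoscopy, is scored as no ulcer although the outcome is known. This follows from the wording of the End points section and needs no numerical assumption.

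The size rests on two assumptions: equal allocation, and very few such cases. Each case is worth 0.6 percentage points of one arm. The number may be zero, and no effect on the treatment comparison has been shown in either direction. Severity is minor. The reason to act is that misclassification is certain whenever such a case occurs, and that preventing it costs almost nothing.

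**What to change.** Reword the Protocol, End points, in three respects:

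1. An ulcer documented by surgery, by imaging evidence of perforation, or at autopsy, where no endoscopy was done, counts as a primary event if the adjudication committee confirms it. State that the committee is kept unaware of treatment assignment.
2. The 0.5 cm forceps criterion applies to ulcers assessed by endoscopy.
3. The assumed-normal rule does not apply to a patient with an ulcer documented in one of these other ways.

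It would also help to say how a patient is scored who has an ulcer found at operation and a later normal endoscopy, since the present text leaves that patient to the endoscopic result.

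The cost is a small protocol amendment. The committee already exists and would read operative, imaging or autopsy reports from routine care. No procedure is added and patient management does not change. The downside is that a few events would have no forceps measurement; reporting how many primary events were established without endoscopy, by arm, would make this visible.

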## INTRODUCTION

Platelet activation and aggregation play an important role in the pathogenesis of arterial thrombosis and lead to ischemic events. Thienopyridine (clopidogrel or ticlopidine) inhibits platelet function by selectively and irreversibly blocking the adenosine diphosphate (ADP) receptor on platelets, thereby affecting ADP-dependent activation of the GpIIb-IIIa complex, the major receptors for fibrinogen present on the platelet surface. Alone or in association with aspirin, clopidogrel is a thienopyridine, which has successfully proved to be beneficial in the treatment of acute coronary syndrome and prevention of ischemic events in patients with atherosclerotic diseases.

The CAPRIE study showed that long-term administration of clopidogrel to patients with atherosclerotic vascular disease is more effective than aspirin in reducing the combined risk of ischemic events. Additionally, Clopidogrel induced fewer episodes of gastrointestinal bleeding than aspirin. The American College of Cardiology-American Heart Association guidelines therefore recommend clopidogrel as an alternative to aspirin for patients with unstable angina or non-ST-segment elevation myocardial infarction who have an aspirin intolerance.

However, a recent study from our center demonstrated that 11% of the patients with a peptic ulcer history who took clopidogrel for the prevention of ischemic events had recurrent peptic ulcer during a 6-month follow-up period. Another prospective study also showed 9% of patients with a history of peptic ulcer bleeding who took clopidogrel had recurrent ulcer bleeding within

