Recently, the interaction of PPIs and thienopyridines has raised the concern for the safety of combination use of the two medicines. Thienopyridines are prodrugs, which must be absorbed in the gastrointestinal tract, and metabolized in the liver to generate active metabolites and acquire their anti-platelet properties. The metabolism of thienopyridines involve CYP2C19 isoenzyme, which is also the key enzyme for the metabolism of most PPIs. This has led to the assumption that some PPIs may potentially inhibit the CYP2C19 pathway and interfere with the conversion of thienopyridines to active form. Three large retrospective observation studies also reported that patients prescribed clopidogrel who also took PPIs had significant increases in cardiovascular events. However, Bhatt et al. recently conducted a double-blind, prospective randomized trial (COGENT; Clopidogrel and the Optimization of Gastrointestinal Events Trial) to investigate the effect of omeprazole in patients receiving both aspirin and clopidogrel. The data demonstrated that prophylactic use of omeprazole reduces the rate of upper GI bleeding among patients receiving aspirin and clopidogrel, and there were no differences in CV events between omeprazole and placebo groups.

Our recent study demonstrated that esomeprazole does not influence the action of clopidogrel on platelet aggregation when doses of esomeprazole and clopidogrel are widely separated. However, whether H2RA may interfere with the conversion of thienopyridines to active form remain unclear. Therefore, we design the randomized double-blind comparison study to investigate whether proton pump inhibitor is superior to H2RA in the prevention of recurrent peptic ulcers in thienopyridine users.

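### Patients with no follow-up endoscopy are counted as ulcer-free, which understates ulcer rates and biases the comparison if the unexamined share differs by arm

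*Protocol*

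**What the plan says.** Three statements in the protocol's End points section matter here. The outcome is endoscopic: "The primary end point is the occurrence of gastric and/or duodenal ulcers, as determined by endoscopy, during the 6-month study period". The events that count are then restricted: "Only events that are confirmed by the adjudication committee and that occurred during treatment are included in the analysis". Patients never examined are assigned a result: "Patients who do not have follow-up endoscopic examination are assumed to have had normal findings".

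Under Follow-up, endoscopy is "performed whenever persistent dyspepsia, severe epigastric pain, hematemesis or melena occurred and at the end of the 6th month". The month-6 examination therefore applies to everyone, with or without symptoms. The same section says of the monthly visits: "Upper gastrointestinal and cardiovascular symptoms are assessed at each visit".

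The Introduction acknowledges that ulcers can be silent. It cites a six-month recurrence figure from the same centre of "11% of the patients with a peptic ulcer history who took clopidogrel". It also describes the trial's purpose and blinding: "we design the randomized double-blind comparison study to investigate whether proton pump inhibitor is superior to H2RA".

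**The concern.** The rule gives unexamined patients an ulcer risk of exactly zero, and nothing in the protocol supports that. Silent ulcers are acknowledged and month-6 endoscopy is scheduled for all, so a lack of symptoms cannot stand for a lack of ulcer.

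The direction of the error is not fixed, so the rule cannot be called conservative. More unexamined patients on famotidine hides a true advantage of pantoprazole. More on pantoprazole enlarges an advantage or creates one. Chance imbalance alone does not raise type I error; the unexamined share has to depend on treatment. Blinding makes a large dependence unlikely. One route survives it: dyspepsia triggers endoscopy, and either study drug may change dyspepsia. The protocol does not show that this will happen.

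A second difficulty lies in the same paragraph. Events count only if they occur during treatment, while the end point covers the six-month study period. For a patient who stops early and is never examined, it is unclear which outcome, over which period, is being assumed normal.

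**Working it through.** **Inputs.** From the protocol: 334 patients, and 11% recurrence over six months (Introduction, clopidogrel users with an ulcer history). Assumed: 1:1 allocation (167 per arm), 11% on famotidine and 3% on pantoprazole, pooled z-test at two-sided 5%, and the unexamined shares shown. The protocol at hand attaches no design rates or drop-out to the 334, so there is no figure of the plan's own to reproduce. The point does not depend on one.

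**Formula.** Let p be the true rate, m the unexamined share and k the risk in unexamined patients divided by that in examined patients. The examined rate is e = p / [(1 − m) + k·m]. The rule records e(1 − m), which equals p only if m = 0 or k = 0. At k = 1 it is p(1 − m): for p = 11%, the recorded rate is 10.45%, 9.9% and 8.8% at m = 5%, 10% and 20%. At k = 0.5 and m = 20%, e = 11/0.9 = 12.22% and the recorded rate is 12.22 × 0.8 = 9.78%.

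On-demand endoscopy and the on-treatment restriction probably put k below 1, so k = 1 is near an upper bound. Power, type I error and Wald coverage below come from exact enumeration of two binomials.

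**Equal unexamined shares, true difference 8.0 points**

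| m in both arms | k | Difference under rule | 95% CI coverage | Power: rule v examined-only |
|---|---|---|---|---|
| 10% | 1 | 9.9 − 2.7 = 7.2 | 92.4% | 79.8% v 79.8% |
| 20% | 1 | 8.8 − 2.4 = 6.4 | 87.2% | 74.6% v 75.5% |
| 10% | 0.5 | 7.6 | 93.7% | 82.0% v 82.0% |
| 20% | 0.5 | 7.1 | 92.0% | 79.3% v 80.5% |

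The risk ratio stays at 0.273 (2.7/9.9 = 3/11). At k = 1 the standard error of the difference is 2.63 and 2.49 points under the rule, against 2.91 and 3.08 in examined patients only. Thus the interval narrows as information is lost. With complete data, power is 84.2%; nearly all of the fall comes from the missing examinations, not from the rule.

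**Unequal shares, same true rates, k = 1.** The recorded risk ratio is the true one times (1 − m_P)/(1 − m_F).
- 20% on famotidine, 10% on pantoprazole: factor 0.9/0.8 = 1.125; difference 8.8 − 2.7 = 6.1 points; coverage 85.3%; power 68.7% v 79.0% examined-only.
- 10% and 20%: factor 0.8/0.9 = 0.89; difference 9.9 − 2.4 = 7.5 points.
- 5% and 25%: difference 10.45 − 2.25 = 8.2 points, now overstated.

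**No true effect, 11% in both arms.** The last column is the difference in shares divided by √[2m̄(1 − m̄)/167], where m̄ is their mean.

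| Unexamined, famotidine v pantoprazole | Rule, k = 1 | Rule, k = 0.5 | Examined-only, k = 0.5 | Imbalance in SE |
|---|---|---|---|---|
| 5% v 10% | 5.5% | 5.2% | 5.0% | 1.7 |
| 10% v 20% | 6.5% | 5.6% | 5.3% | 2.6 |
| 5% v 25% | 10.8% | 6.9% | 6.5% | 5.1 |

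With none missing, type I error is 5.1%. At k = 0.5 the examined-only analysis errs in the opposite direction to the rule.

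**Would imputation help?** A simulation (20,000 runs, 30 imputations) assumed symptoms in 60% of ulcer and 20% of non-ulcer patients, with symptomatic patients one tenth as likely to be unexamined.
- 20% unexamined in both arms: the rule reads 7.1 points, examined-only 8.8 and imputation by arm and symptoms 8.0. Coverage is 91.7%, 94.4% and 94.6%.
- No effect, 5% v 25% unexamined: type I error is 7.1%, 6.1% and 5.1%.
- Symptoms uninformative, ulcer patients half as likely to be unexamined, 20% unexamined (12,000 runs): 7.2, 8.9 and 8.9 points.

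**The case against.** The strongest reply is that materiality is assumed. The protocol gives no expected unexamined share and no reason for it to differ by arm. Blinding, monthly visits and month-6 endoscopy for all work against a difference. The 11% comes from an earlier study, while both arms here receive an active drug. With a null rate of 5% and 10% v 20% unexamined, the rule gives 5.5% at k = 1 and 5.1% at k = 0.5, against 4.9% with none missing. All of this stands. It limits the size of the bias, not its existence.

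The second reply is that imputation is not clearly better. It recovers 8.0 points because the simulation lets symptoms explain the missingness. When they do not, it overstates by about 0.9 points where the rule understates by about 0.8, and overstating is the less welcome error in a superiority trial. At k = 0.25, null 11% and 5% v 25% unexamined, the rule gives 5.7% and examined-only 8.7%. Patients who leave follow-up may also lack the later symptom records. This stands too, and is why a tipping-point analysis belongs beside the imputation. It does not justify a primary analysis that treats an unknown outcome as known.

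The SAP, which is not at hand, may add sensitivity analyses. The protocol, however, has already fixed how these patients are counted for the primary end point.

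**Conclusion.** The concern holds. The protocol fixes a rule that understates absolute ulcer rates whenever an unexamined patient has an ulcer. With similar missingness it understates the risk difference and gives too narrow an interval. With treatment-related missingness it biases the comparison in either direction. Nothing else in the protocol corrects this.

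The size runs from negligible to material. In the equal-share cases examined, 0.4 to 1.6 points of an 8.0-point difference are lost and coverage falls to between 93.7% and 87.2%. Type I error at 10% v 20% unexamined is 5.6% to 6.5%; the 10.8% figure needs an imbalance that is unlikely under blinding. These results rest on the assumed rates, allocation, unexamined shares and values of k. The rule should be changed, but it does not undermine the design. Confidence in the bias is high; confidence in its size is moderate at best.

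**What to change.** Replace the sentence in End points with text to this effect:

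> *Patients without follow-up endoscopy have a missing primary outcome. The primary analysis includes all randomised patients and uses multiple imputation with a small model containing treatment arm and the symptoms recorded at the monthly visits.*

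In the same paragraph, reconcile this with the restriction to events during treatment, so that the outcome imputed for a patient who stops early is the one counted in examined patients, over the same period. Keep the present rule as a labelled sensitivity analysis and add a tipping-point analysis that varies the assumed risk in unexamined patients separately by arm. The form of the model can be left to the SAP.

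The cost is small. No extra patients or visits are needed, because symptoms are already assessed monthly. The interval becomes somewhat wider: simulated mean width is about 11.1 and 11.6 points at 10% and 20% unexamined, against about 10.5 and 10.3 under the rule. The model must stay small, since about 0.03 × 167 = 5 pantoprazole ulcers are expected at the assumed 3%. It must also allow for incomplete symptom records in patients who leave follow-up.
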